### **Visit 2, Day 3-5:**

The following will be undertaken, and results recorded:

Obstetric examination\* (foetal movement and foetal heart rate), vital signs, safety laboratory tests, assessment of the injection site and review of the eDiary incl. if measured temperatures within 72 hours lead to permanent discontinuation of vaccination (Section 4.7.2), transfer of AEs and CMs to the eCRF (and instruct to continue eDiary recording). This visit may be planned as a home visit.

### **Visit 3, Day 26-30:**

The following will be undertaken, and results recorded:

Targeted physical examination\* (respiratory, cardiovascular), obstetric examination\* (fundal height, foetal movement, and foetal heart rate), vital signs (pre- and 30 minutes post-vaccination), urinalysis, safety laboratory tests, assessment of the (previous) injection site, review of the eDiary incl. transfer of AEs and CMs to the eCRF (and instruct for next 7-day-eDiary recording period), check contraindications (Section 4.7.2), assessment of safety laboratory test results from Visit 2, pre-vaccination immunogenicity maternal blood sample, and injection of vaccine/placebo. Before the subject leaves the site: Assessment of the (new) injection site and check immediate adverse reactions.

### **Visit 4, Day 31-33:**

The following will be undertaken, and results recorded:

Obstetric examination\* (foetal movement and foetal heart rate), vital signs, safety laboratory tests, assessment of the injection site(s) and review of the eDiary incl. if measured temperatures within 72 hours lead to permanent discontinuation of vaccination (Section 4.7.2), transfer of AEs and CMs to the eCRF (and instruct to continue eDiary recording). This visit may be planned as a home visit.

### **Visit 5, Day 54-58:**

The following will be undertaken, and results recorded:

Targeted physical examination\* (respiratory, cardiovascular), obstetric examination\* (fundal height, foetal movement and foetal heart rate), vital signs (pre- and 30 minutes post-vaccination), urinalysis, safety laboratory tests, assessment of the (previous) injection sites, review of the eDiary incl. transfer of AEs and CMs to the eCRF (and instruct for next 7-day-eDiary recording period), check contraindications (Section 4.7.2), assessment of safety laboratory test results from Visit 4, pre-vaccination immunogenicity maternal blood sample, and injection of vaccine/placebo. Before the subject leaves the site: Assessment of the (new) injection site and check immediate adverse reactions.

### **Visit 6, Day 59-61:**

The following will be undertaken, and results recorded:

Obstetric examination\* (foetal movement and foetal heart rate), vital signs, safety laboratory tests, assessment of the injection sites and review of the eDiary incl. transfer of AEs and CMs to the eCRF (and instruct to continue eDiary recording). This visit may be planned as a home visit.

### Visit 7, Day 82-86:

The following will be undertaken, and results recorded:

Obstetric examination\* (fundal height, foetal movement and foetal heart rate), height (from screening) and weight (for calculation of BMI), vital signs, safety laboratory tests, immunogenicity maternal blood sample, assessment of the injection sites and review of the eDiary incl. transfer of AEs and CMs to the eCRF (and instruct how to end the eDiary).

### Visit 8, Delivery:

The following will be undertaken within 72 hours of delivery, and results recorded:

Vital signs, urinalysis, immunogenicity maternal blood sample, [REDACTED], and AE and CM check (only medically attended adverse events (MAAEs), adverse events of special interest (AESIs) e.g., GBS disease, autoimmune disease and immune-mediated reactions, or SAEs, and related CMs), according to Table 2.

If a participant delivers, following the first vaccination but before completing all of the pre-delivery follow-up visits, additional blood samples will be collected at delivery for safety laboratory tests.

### Visit 9, Day 24-32 Post-delivery:

Targeted physical examination\* (respiratory, cardiovascular), height (from screening) and weight (for calculation of BMI), vital signs, urinalysis, [REDACTED], and AE and CM check (only MAAEs, AESIs or SAEs and related CMs), according to Table 2. This visit may be planned as a home visit.

### Visit 10, Day 84-96 Post-delivery:

Vital signs, [REDACTED] and AE and CM check (only MAAEs, AESIs or SAEs and related CMs), according to Table 2. This visit may be planned as a home visit.

### Visit 11, Day 166-194 Post-delivery / End-of-study visit:

Full physical examination (respiratory, cardiovascular, gastrointestinal, gross central nervous system, gross musculoskeletal) by a physician, height (from screening) and weight (for calculation of BMI), vital signs, urine pregnancy test (any participant found pregnant at the end of the study will be followed until delivery, as regards if their baby is healthy at delivery). AE and CM check (only MAAEs, AESIs or SAEs and related CMs), according to Table 2. This visit may be planned as a home visit.

**\*Targeted physical examinations and obstetric examinations of mothers should be performed by appropriately qualified site staff e.g., physician, midwife or nurse.**

## VISITS FOR BABIES:

### Visit 8, Delivery:

The following will be undertaken, and results recorded:

Demography, gestational history (gestational age and gender), physical examination\*, head circumference, length, weight, Apgar score (Apgar score at 1, 5 and 10 minutes, available scores will be collected, ‘not recorded’ will be an option), vital signs (heart rate), immunogenicity cord blood sample (or infant blood sample – heel prick or venous, within 72 hours of birth, if cord blood sample not possible, for target blood volumes for babies see Section 4.4), and AE and CM check.

### Visit 9, Day 24-32, Post-delivery:

The following will be undertaken, and results recorded:

Physical examination\*, head circumference, length, weight, vital signs, developmental milestones, immunogenicity infant blood sample (heel prick or venous, for target blood volumes for babies see Section 4.4), and AE and CM check. This visit may be planned as a home visit.

### Visit 10, Day 84-96, Post-delivery:

The following will be undertaken, and results recorded:

Physical examination\*, head circumference, length, weight, vital signs, developmental milestones, immunogenicity infant blood sample (heel prick or venous, for target blood volumes for babies see Section 4.4), and AE and CM check (only MAAEs, AESIs e.g., abnormal development according to developmental milestones, or SAEs, and related CMs), according to Table 3. This visit may be planned as a home visit.

### Visit 11, Day 166-194, Post-delivery / End-of-study visit:

The following will be undertaken, and results recorded:

Physical examination\*, head circumference, length, weight, vital signs, developmental milestones, and AE and CM check (only MAAEs, AESIs or SAEs, and related CMs), according to Table 3. This visit may be planned as a home visit.

***\*Physical examinations of babies should be performed by appropriately qualified site staff e.g., physician, midwife or nurse.***

### 4.3.3 Safety assessments

The safety of the GBS-NN/NN2 vaccine will be assessed through collection of adverse events (AEs) in electronic diaries up to 7 days following each administered vaccination, as well as through laboratory safety tests, physical examinations and vital signs performed at the study visits. The safety assessments at the study visits cover both the mother and the baby.

AEs in the mother are assessed from the time the informed consent is signed until Day 84. From Delivery (Visit 8) and onwards, only MAAEs, AEs of special interest (AESI), e.g., GBS disease, autoimmune disease and immune-mediated reactions, or SAEs are assessed.

Any participant found to be pregnant at the end of the study will be followed up, as regards if their baby is healthy at delivery.

For the babies, all AEs will be assessed for the first 28 days of life, after this only MAAEs, AESIs e.g., GBS disease, abnormal development according to developmental milestones, or SAEs.

For further details, see Table 2 for mothers, and Table 3 for babies.

AEs with onset before the first administration of investigational product in a subject are defined non-treatment emergent AEs, and AEs with onset after the first administration of investigational product are defined treatment emergent AEs.

#### 4.3.3.1 Diaries

The subject will get access to an electronic diary (eDiary) at the study visit where vaccine/placebo is administered. In the eDiary, details of solicited local and systemic reactions will be recorded, for 7 days after each of the vaccinations (the day of the vaccination and the following 6 days).

For solicited local injection site reactions (*redness, swelling, pain, tenderness, itching*) and *pyrexia* (oral temperature  $>37.9^{\circ}\text{C}$ ), the diameters and temperatures will be measured, by use of rulers and thermometers, and recorded in the eDiary.

For solicited systemic reactions (*nausea, vomiting, diarrhoea, headache, fatigue, myalgia*), intensities (*mild, moderate, or severe*) will be recorded in the eDiary. In addition, other AEs, i.e., unsolicited AEs, including MAAEs, SAEs, concomitant medication (CM) or vaccines will also be recorded and assessed in the eDiary.

The solicited local and systemic reactions, recorded in the eDiary, will be assessed by the site staff.

If serious, the SAEs will undergo evaluation as per the current reference safety information of the IB, as described in section 6.

Details on *new medical problems* (unsolicited AEs), *visits to a doctor* (MAAEs) or *visits to a hospital* (SAEs) or *new medication* (CM) recorded in the diary will be assessed by the investigator at the visits 28 days following each vaccination, as described in section 6.

#### 4.3.3.2 Safety laboratory tests

Safety laboratory testing for all subjects (mothers) will be performed at screening, 4 $\pm$ 1 and 28 days after the vaccinations and on Day 84, the last pre-delivery visit. If a participant delivers after Day 0, but before completing all pre-delivery visits, additional safety laboratory tests will be taken at delivery. There is urinalysis (specific gravity, pH, protein, glucose, ketones, occult blood, leukocyte esterase, nitrites) at screening, all vaccination visits, at delivery and 28 days post-delivery. If the urinalysis 'dipstick' test result is positive for nitrite and/or 2+ or more reported for protein, blood, and/or leucocytes, then urine microscopy and/or culture will be performed.

The results of the safety laboratory testing, and urinalysis will be assessed, and abnormal results will be classified as clinically significant (CS) or not clinically significant (NCS). CS results will be reported as AEs or SAEs, if the criteria for seriousness are met, please see Section 6.1.

The safety laboratory tests in this study are:

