###### Visit 1, Day 0: Randomisation, 21+0 to 23+6 weeks GA:

Eligibility check - participants who remain eligible will be randomised according to the randomisation schedule. The randomisation will allocate participants to a specific group. Visit 1, Day 0, is at the planned time of the 1st vaccination which is 21+0 to 23+6 weeks GA, as established by first/second trimester ultrasound examination.

Only unblinded study team members, responsible for dispensing and injecting vaccines/placebo, or for checking related procedures and records, will have access to any information regarding the actual products injected to the subjects, and this information will not be revealed to blinded study team members.

The actual injection of vaccine/placebo will be performed by unblinded study team members, or alternatively by blinded study team members by use of syringes with opaque tape, to avoid unblinding during the injections.

The following will be undertaken, and results recorded:

Targeted physical examination\* (respiratory, cardiovascular), obstetric examination\* (fundal height, foetal movement and foetal heart rate), vital signs (pre- and 30 minutes post-vaccination), urinalysis, pre-vaccination immunogenicity maternal blood sample, and injection of vaccine/placebo. Before the subject leaves the site: Assessment of the injection site, check immediate adverse reactions, and give access to and instruct in the 7-day-eDiary.

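### Visits 4 and 6 are counted from Day 0 and not from the injection, so Table 2 permits the early post-dose safety labs 1 to 7 days after doses 2 and 3, where section 4.3.3.2 requires 4±1 days

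*Protocol*

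**What the plan says.** Protocol section 4.3.3.2 ties the early safety laboratory tests to the injection. They are due at 4±1 days "and 28 days after the vaccinations and on Day 84, the last pre-delivery visit".

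The visit schedule ties them to study day. In section 4.3.2, "Visit 1, Day 0, is at the planned time of the 1st vaccination which is 21+0 to 23+6 weeks GA", and the later visits are numbered from that day:

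- dose 2 at "Visit 3, Day 26-30", followed by labs at "Visit 4, Day 31-33"
- dose 3 at "Visit 5, Day 54-58", followed by labs at "Visit 6, Day 59-61"

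Protocol Table 2 and SAP Table 2 carry the same windows. Visit 2 (Day 3-5) follows a dose that is always on Day 0, so it is in effect counted from the injection.

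Visit 4 also includes an eDiary review, "incl. if measured temperatures within 72 hours lead to permanent discontinuation of vaccination (Section 4.7.2"). The same check is written for Visit 2. It is not written for Visit 6.

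Section 4.7.2 allows a dose to be postponed for acute infection or fever. Neither that section nor the schedule says what then happens to the follow-up visit. SAP section 5 lists visit intervals and overdue visits, the latter reckoned from the previous visit, among the items monitored centrally, but it defines no interval.

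**The concern.** Two parts of the protocol give different rules for the same blood sample. A woman dosed on Day 30 and seen on Day 31 is inside both Table 2 windows, yet her sample is 1 day post-dose. A woman dosed on Day 26 and seen on Day 33 is also inside both, at 7 days. Neither sample meets section 4.3.3.2. Nor would the first criterion one might look to in section 7.5 pick them up: it refers to a week's departure from schedule, and these visits do not depart from the Table 2 windows.

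Laboratory tests are part of the key secondary safety endpoint, and SAP section 4.7.3 summarises them by visit and treatment group without a variable for time since injection. The Visit 4 column of those tables may therefore mix samples taken at 1 day with samples taken at 7, and the reader could not tell. The Visit 4 labs are also those assessed at Visit 5 before the third injection (Table 2, footnote j).

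For the 72-hour temperature review, the worry is that a Visit 4 held 1 or 2 days after the dose cannot assess a period that is still running.

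**Working it through.** **Inputs.** Required gap from injection to early labs: 4±1, so 3 to 5 days (protocol 4.3.3.2). Dose days: 0, 26-30 and 54-58 (Visits 1, 3, 5). Early lab visits: Day 3-5, 31-33 and 59-61 (Visits 2, 4, 6). All windows are from protocol Table 2 and section 4.3.2.

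**Formula.** Gap = visit day − dose day.

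**Step 1: the plan's own figure.** With doses on nominal Days 0, 28 and 56:

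- Visit 2: 3−0 = 3 to 5−0 = 5
- Visit 4: 31−28 = 3 to 33−28 = 5
- Visit 6: 59−56 = 3 to 61−56 = 5

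So 4±1 reproduces across the whole visit window only when dose 2 is exactly on Day 28 and dose 3 exactly on Day 56.

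**Step 2: the full permitted dose windows.**

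| Dose 2 day | Gap if Visit 4 is on Day 31 / 32 / 33 | Visit days that also meet 4±1 |
|---|---|---|
| 26 | 5 / 6 / 7 | 31 |
| 27 | 4 / 5 / 6 | 31, 32 |
| 28 | 3 / 4 / 5 | 31, 32, 33 |
| 29 | 2 / 3 / 4 | 32, 33 |
| 30 | 1 / 2 / 3 | 33 |

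The shortest gap is 31−30 = 1 day and the longest is 33−26 = 7 days. Of 5 × 3 = 15 pairs, 1+2+3+2+1 = 9 lie at 3-5 days, 3 are shorter and 3 are longer, so 6/15 (40%) lie outside. Dose 3 and Visit 6 give the same table shifted by 28 days: 59−58 = 1 to 61−54 = 7, again with 9, 3 and 3.

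**Step 3: can both rules be met?** Yes. The last column is never empty, but at the extremes only one day remains (dose on Day 26: Day 31; dose on Day 30: Day 33).

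**Step 4: the 72-hour review at Visit 4.** The three short pairs (dose Day 29 with visit Day 31; dose Day 30 with visit Day 31 or 32) have gaps of 2, 1 and 2 days, all under 72 hours. A gap of 3 calendar days may also fall slightly short of 72 elapsed hours, but that applies equally to Visit 2.

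**Step 5: what follows Visit 4.** The diary covers the vaccination day and the next 6 days (section 4.3.3.1), so after a Day 30 dose it runs to Day 36. Visit 4 tells the woman to continue recording. Visit 5 is at least 54−33 = 21 days after an in-window Visit 4. Its eDiary review and section 4.7.2 contraindications check come before the injection.

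**Step 6: postponed doses.** Section 4.7.2 defers a dose until 7 days after an acute infection resolves. As an illustration, an infection resolving on Day 28 moves dose 2 to 28+7 = Day 35 or later, when the Visit 4 window has already closed (33−35 = −2 days). No section says where Visit 4 then falls.

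**The case against.** The strongest reply is that section 4.3.3.2 is itself binding. A Day 31 sample after a Day 30 dose is not fully compliant: it meets Table 2 and breaches the text. Since both rules can be met for every in-window dose day, a site that reads both has a workable schedule, and SAP section 5 has visit intervals under central monitoring. This stands, and it limits the point to loose drafting of the windows. It does not remove it, because no document tells sites which rule governs and the monitoring item sets no interval.

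Five stronger readings are tempting, and the documents do not support them.

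- *That 40% of women would be mistimed.* The 6 of 15 counts permitted day pairs as if equally likely. The documents give no distribution of actual visit days.
- *That the 72-hour review is undermined at both visits.* It is written for Visit 4 and not for Visit 6, and no injection follows Visit 5.
- *That a woman meeting the fever criterion could receive dose 3 unnoticed.* The Visit 5 checks come first, with the diary complete.
- *That the arms are biased against each other.* All five arms share one schedule under observer blinding, and the lab summaries are descriptive and by visit. The first active dose comes at Visit 1 in Groups 2 and 3 and at Visit 3 in Groups 1 and 4, so an informal comparison after first active dose would mix regimen with sampling time. The SAP plans no such lab comparison; its tables by vaccination number cover solicited events only.
- *That laboratory values differ materially between 1, 4 and 7 days post-dose.* The documents offer no figure on this.

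**Conclusion.** The inconsistency is real. For doses 2 and 3, Table 2 permits early safety labs at 1 to 7 days post-dose where section 4.3.3.2 says 3 to 5. After dose 1 the two agree. Postponed doses are left without any follow-up anchor.

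The consequence is modest. A key secondary safety measure may not follow its stated timing after two of the three injections, and the planned tables would not show it. At Visit 4 alone, the temperature review can be premature, with a later check still ahead of dose 3.

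The result rests on the windows as printed and on whole-day counting. It assumes that no operational document outside those reviewed already counts Visits 4 and 6 from the injection. The point merits correction because the remedy is cheap. It does not call the primary analysis into question.

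**What to change.** 1. **Protocol and SAP schedule.** Reconcile section 4.3.3.2 with the Visit 4 and Visit 6 windows in protocol Table 2, section 4.3.2 and SAP Table 2. State whether these visits are counted from Day 0 or from the actual injection, and what applies after a dose postponed under section 4.7.2. Counting from the actual injection, as Visit 2 in effect already is, is one way to do this; the timing is for the sponsor to decide.
2. **SAP section 4.7.3.** Derive days since last injection for each post-dose laboratory sample from the dosing and sampling dates. Use it to flag, or summarise separately, samples outside the stated 4±1 days. This is useful whichever anchor is chosen, and also for data already collected.

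**Cost.** A small change to a few places in the protocol and SAP, the matching visit windows in the eCRF, and one derived variable. There is no extra visit or sample. If the change is judged substantial, protocol section 12 requires notification to and approval by the authorities and ethics committees, here in three countries. The SAP derivation does not change the schedule and could proceed separately.

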**Haematology:**

Red blood cell count, haemoglobin, haematocrit, platelet count, MCV, MCHC, white blood cell count with absolute differential (neutrophils, lymphocytes, monocytes, eosinophils, basophils) counts

**Biochemistry:**

Sodium, potassium, blood urea, creatinine, creatine kinase, glucose, calcium, albumin, cholesterol, C-reactive protein, triglycerides, phosphorus (inorganic phosphate), lactate dehydrogenase, total protein, globulin, uric acid, alkaline phosphatase, aspartate aminotransferase, alanine aminotransferase, gamma-glutamyl-transferase, total bilirubin and direct bilirubin

#### **4.3.3.3 Physical examinations and vital signs in mothers and babies**

As part of the safety assessments, for the mothers, there is a full physical examination (respiratory, cardiovascular, gastrointestinal, gross central nervous system, gross musculoskeletal) at screening and at 6 months post-delivery, and targeted physical examinations (respiratory, cardiovascular) before each administration of vaccine, and 28 days post-delivery.

Obstetric examinations [fundal height (no fundal height at visits 2, 4 and 6), foetal movement and foetal heart rate] is performed at all pre-delivery visits for mothers.

Vital signs (heart rate, blood pressure and oral temperature) are measured at all study visits for mothers. At the study visits where vaccine is administered, the vital signs are measured before the vaccination and again 30 minutes post-vaccination prior to leaving the site.

At all vaccination visits the injection sites will be inspected and assessed by the site staff before the subject leaves the site. Photographs may be taken, as required to document unexpected reactions.

In case of identification of a new medical condition (or an increase in intensity/frequency of a condition existing at screening) in the mothers, these will be recorded as AEs, as specified in Table 2.

At birth babies are physically examined and weight, length, head circumference and Apgar score at 1, 5 and 10 minutes, as available, are measured. The babies are physically examined at all baby study visits, as specified in Table 3.

In addition to physical examinations, baby assessments include developmental milestones (age-appropriate developmental milestone checks) and vital signs (heart rate), at all baby study visits after birth, assessing the safety and wellbeing of the babies. If medical conditions are identified in the babies, these will be recorded as AEs, as specified in Table 3.

#### **4.3.4 Immunogenicity assessments**

In this study the immunogenicity assessments are both related to the study participants (the mothers) and to their babies. In the mothers, pre-specified vaccine induced immune response markers are measured, whereas in the babies, the same immune markers, obtained through passive transport from the mothers to the babies, are measured.

Quantitative ELISAs are used for detection of IgG specific to the AlpN proteins (RibN, Alp1N, Alp2/3N or AlpCN) and IgG specific to the vaccine fusion proteins (GBS-NN and GBS-NN2) in serum samples, using a calibrated reference standard produced from pooled selected sera from previous studies with GBS-NN and GBS-NN/NN2 which contains IgG specific to the individual AlpN domains and the fusion proteins.

In the primary immunogenicity analysis, concentrations of IgG antibodies, specific to the AlpN proteins from cord blood samples taken at delivery/birth are evaluated and compared between the groups, through calculations of geometric mean concentrations and proportions of subjects with IgG concentrations above the pre-defined thresholds.

The secondary immunogenicity measurements of IgG from maternal blood samples taken at 4 weeks after each vaccination and at delivery are evaluated and compared, including calculation and evaluation of ratios of IgG antibody concentrations between maternal and cord/baby blood at delivery.

IgG measurements from infant blood samples taken at 28 days and 3 months of age, are used for calculation of geometric mean concentrations and proportions of babies with IgG concentrations above pre-defined thresholds as part of the secondary immunogenicity analysis.

A large rectangular area of the page is completely blacked out, indicating redacted content. The redaction is bounded by a thin yellow border.

